**Does Vitamin C Reduce Finger Stiffness after
Distal Radius Fractures: a Placebo Randomized
Controlled Trial.**

NCT02216812

**Version Date of the Document: 22 February
2017**

PARNTERS HUMAN RESEARCH
DETAILED PROTOCOL

Does Vitamin C Reduce Finger Stiffness after Distal Radius Fractures: a Placebo Randomized Controlled Trial.

Version 4
2-22-2017

BACKGROUND & SIGNIFICANCE

The reported prevalence of disproportionate pain and disability among patients recovering from a fracture of the distal radius varies widely, between 1% and 37% in published series,¹⁻⁷ perhaps in part because it is poorly defined, known by so many different names, subjective, and unverifiable. In general, physicians ascribe disproportionate pain and disability to a poorly understood pathophysiologic process currently labeled “complex regional pain syndrome”, while psychologists understand this as ineffective coping strategies.⁸ Studies consistently identify psychological factors (catastrophic thinking in particular) as the most important determinants of pain intensity, finger stiffness, and magnitude of disability after distal radius fractures.^{8,9}

Along these lines, it is difficult to interpret the trials suggesting that vitamin C limits the occurrence of complex regional pain syndrome, given that the diagnosis is subjective and variably defined, and the only published trials were performed by advocates of vitamin C.^{6,10} We see this reflected in clinical practice, as only 11% of the orthopaedic surgeons always prescribes vitamin C after a distal radius fracture, making it one of the least adhered to recommendations of the AAOS clinical practice guidelines.¹¹ In addition, there is a lack of clarity regarding the mechanism by which vitamin C would decrease the incidence of complex regional pain syndrome.¹² We are interested in the effect of vitamin C after distal radius fractures on objective measurement of finger motion, patient reported outcome measures, and pain intensity, instead of the previously used, subjective and imprecise Veldman criteria for complex regional pain syndrome¹³, i.e., (i) unexplained diffuse pain, or (ii) edema, (iii) difference in skin color, or (iv) temperature, or (v) limited active range of motion.

SPECIFIC AIMS

Primary null hypothesis

There is no difference in finger stiffness (distance to palmar crease) between patients taking vitamin C or placebo after six weeks after a distal radius fracture.

Secondary null hypotheses

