There is no difference in PROMIS upper extremity function and pain score between patients taking vitamin C or placebo after a distal radius fracture.

There are no factors associated with finger stiffness, PROMIS upper extremity function, and pain intensity after fracture of the distal radius.

SUBJECT SELECTION

Patients will be enrolled in the outpatient clinic at the Hand & Trauma Services at Massachusetts General Hospital.

Inclusion Criteria:

- All adult (age 18 or greater) patients presenting to the Hand and Orthopaedic Trauma Services of the Massachusetts General Hospital (MGH) within two weeks of a fracture of the distal radius, either operatively or nonoperatively treated.

Exclusion criteria:

- Patients with severe kidney failure or kidney stones, known allergy for vitamin C or pregnancy, or patients who are not fluent in either English or Spanish.
- Wrist fracture within the last year on the newly fractured side
- Confounders (baseline characteristics): fracture on the dominant side, current vitamin C supplements.

SUBJECT ENROLLMENT

The treating surgeon at the Hand or Orthopedic Trauma service will determine if the patient is eligible to participate in the study. The surgeon will introduce the study to the patient and answer any questions that the patient may have about the study or about randomization. If the patient agrees to participate, a trained research coordinator (pre-med student) or trained research assistant (PhD or medical student) not involved in clinical care, will obtain consent and begin enrollment procedures. As with the other research studies in this department, there will be no coercion. The research coordinator or research assistant will explain to the patient that participation in this study is completely voluntary and that the patient may withdraw at any time. The research coordinator or research assistant will offer all subjects the opportunity to speak with a licensed physician Investigator during the consent process.

Subjects will be given a copy of the informed consent form, and be informed that their participation is voluntary and that they can withdraw at any time during the study. Subjects make take as long as they like to consider participation, provided they still meet all enrollment criteria.

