Study staff will provide the patient with a box of medication, containing either vitamin C or placebo (both completely similar in appearance, taste and smell). The pharmacist involved in preparing the placebo will randomize the boxes of medication according to a list of generated random numbers (Stata 13). The

pharmacist will be the only person with access to the code until conclusion of the trial.

STUDY PROCEDURES

Eligible patient, after informed consent, will be randomly assigned, double-blind, to take either placebo or vitamin C 500 mg for 6 weeks.

At enrollment and 6 weeks (5-8 weeks acceptable) after fracture we will measure: DPC (dig II-V), PROMIS UE CAT, PROMIS pain interference and VAS score; all questionnaires will be filled out in REDCap. If the researcher misses the subject at the 6 week follow-up or if their appointment is outside of the 5-8 week timeframe, three attempts will be made to contact each patient via email and via telephone to complete the 6 week follow-up questionnaires. To address, one of the secondary hypotheses, patients will be contacted 6 months after injury by email; unresponsive patients will be contacted by telephone to assist them with filling out the questionnaires. Three attempts will be made to contact each patient via email and via telephone to complete the follow-up.

Measured variables

At enrollment and 6 weeks (5 to 8 weeks acceptable) after fracture:

- Finger tip distance to palmar crease of fingers II-V (DPC)
- PROMIS Upper Extremity Function (Short form)
- PROMIS Pain Interference Short form
- 0-10 ordinal rating of pain intensity

At 6 months (5 to 8 months acceptable) after fracture:

- PROMIS UE – Short form
- 0-10 ordinal rating of pain intensity

BIOSTATISTICAL ANALYSES

Difference in DPC, function, pain interference and pain will be assessed by Wilcoxon-Mann-Whitney test.

Assuming an effect size of similar magnitude to previous studies¹⁰, power analysis suggests 134 patients provide 80% power to detect a difference with an alpha of 0.05 (effect size 0.50, two tailed Wilcoxon-Mann-Whitney test). As trauma patients are notoriously hard to track, halfway through the study we will assess enrollment and adjust sample size accordingly to account for lost to follow-up.

RISKS AND DISCOMFORTS

Although controversy exists regarding the value of prescribing vitamin C to patients with distal radius fractures, there appears to be limited downside with its use.

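### The only named analysis is an unadjusted rank test; a prespecified model adjusted for the enrollment value, with an estimate and 95% CI, would gain power at no data cost.

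*Combined protocol and SAP*

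**What the plan says.** The primary hypothesis in Specific Aims is "There is no difference in finger stiffness (distance to palmar crease) between patients taking vitamin C or placebo after six weeks after a distal radius". The Biostatistical Analyses section gives one sentence on method: "Difference in DPC, function, pain interference and pain will be assessed by Wilcoxon-Mann-Whitney test". It names no covariate, model, effect measure or interval.

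Study Procedures states: "At enrollment and 6 weeks (5-8 weeks acceptable) after fracture we will measure: DPC (dig II-V), PROMIS UE CAT, PROMIS pain interference and VAS score". The Measured variables list repeats the schedule under "At enrollment and 6 weeks (5 to 8 weeks acceptable) after fracture". Each 6-week outcome therefore has its own enrollment value.

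Under Subject Enrollment, the pharmacist is to "randomize the boxes of medication according to a list of generated random numbers (Stata 13"). No stratification is described.

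Two related items have no analysis attached. The exclusion criteria contain the line "Confounders (baseline characteristics): fracture on the dominant side, current vitamin C supplements". A secondary null hypothesis reads "There are no factors associated with finger stiffness, PROMIS upper extremity function, and pain intensity after fracture of the distal radius", with no list of factors and no method.

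On sample size, the section says "power analysis suggests 134 patients provide 80% power to detect a difference with an alpha of 0.05", for an effect size of 0.50 and a two-tailed rank test.

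**The concern.** A two-sample rank test compares the 6-week values and ignores where each patient started. If stiffness at enrollment predicts stiffness at 6 weeks, part of the outcome variation is explainable, and the plan leaves it in the error term. The trial already collects what is needed to remove it.

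Three things are at stake:

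- **Power.** The sample size has no margin above 80%. No loss rate is given, and the adjustment for loss to follow-up is left until halfway through the study.
- **Chance imbalance.** Without stratification or adjustment, nothing in the stated plan corrects for arms that happen to start at different levels of stiffness.
- **Interpretation.** The background is openly sceptical of earlier vitamin C trials, so a null result is plausible. A p-value alone does not show which effects a null result rules out, or how large a positive one is.

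**Working it through.** **Inputs.** From Biostatistical Analyses: 134 patients, 80% power, two-sided alpha 0.05, effect size 0.50. Assumed because the documents are silent: 1:1 allocation (67 per arm) and r, varied from 0 to 0.6.

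**1. The plan's own figure.** For normal data the Wilcoxon-Mann-Whitney test has efficiency 3/π = 0.955 relative to the t-test. The effective size is 67 × 0.955 = 63.98 per arm. Noncentral-t power at d = 0.50 is 80.1%, and 67 is the smallest number per arm that reaches 80%. So 134 is reproduced exactly, and the sample size is not in error.

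**2. Formula power with adjustment.** Adjusting for baseline multiplies the residual variance by (1 − r²), so effective n per arm = 67 × (3/π) / (1 − r²).

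| r | 1 − r² | Effective n per arm | Power |
|---|---|---|---|
| 0 | 1.00 | 64.0 | 80.1% |
| 0.2 | 0.96 | 66.6 | 81.7% |
| 0.3 | 0.91 | 70.3 | 83.7% |
| 0.5 | 0.75 | 85.3 | 90.1% |
| 0.6 | 0.64 | 100.0 | 94.0% |

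**3. Simulated power.** The tie-corrected planned test was compared with the Wald test of arm in a proportional-odds model with linear baseline. There were 67 per arm, bivariate normal data recorded in 0.25-SD steps, and 4,000 runs per scenario. The Monte Carlo standard error near 80% is √(0.8 × 0.2 / 4,000) = 0.6 points.

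| r | Planned test | Model |
|---|---|---|
| 0 | 80.8% | 81.2% |
| 0.2 | 79.9% | 82.1% |
| 0.3 | 80.5% | 83.9% |
| 0.5 | 80.4% | 90.3% |
| 0.6 | 79.2% | 93.6% |

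If 30% of placebo patients have zero distance (assumption), the figures are 74.0% vs 74.0% (r = 0), 75.0% vs 78.7% (0.3) and 73.9% vs 88.5% (0.6).

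**4. Skewed data with a heavier floor.** Baseline and outcome were skewed, with 40% at zero (assumption), and r is the correlation before skewing and flooring. Planned test versus model: 70.1% vs 69.9% (r = 0), 70.7% vs 72.6% (0.3), 69.0% vs 79.3% (0.6). The gain is smaller, with no real loss at r = 0. The model's type I error in these runs was 4.7–5.5%.

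**5. Overall type I error** (10,000 null runs each at r = 0, 0.3 and 0.6; no floor). The planned test gave 4.6–5.1%. The model gave 5.4% at r = 0 and 0.3, and 5.9% at 0.6. A small part of the power gain at high r reflects this.

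**6. Chance imbalance.** The SD of the baseline mean difference is √(2/67) = 0.173 SD, and 0.25/0.173 = 1.45, so P(|difference| ≥ 0.25 SD) = 0.148. Among null runs that started this unbalanced, the planned test's type I error was 5.3% (r = 0), 7.2% (0.3) and 15.1% (0.6). The model's was 5.6–5.9%.

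**7. Approximate 95% CI half-width for a mean difference.** 1.96 × √[(2/67)(1 − r²)] gives 0.34 SD unadjusted, 0.32 at r = 0.3 and 0.27 at r = 0.6.

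**8. Illustration with losses.** If 20% are lost and not replaced (assumption), 67 × 0.8 = 53.6 remain per arm. Formula power is 70.7% unadjusted, 74.7% adjusted at r = 0.3 and 82.5% at r = 0.5.

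**The case against.** The strongest reply is that nothing here is an error. The planned test is valid under randomisation and correctly powered, so replacing it could be called preference. That is fair as to validity, and it is why this is a recommended improvement rather than a required correction.

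The second reply is that r is unknown. Patients enroll at any time within two weeks of fracture, treated operatively or not. Enrollment stiffness may therefore reflect acute injury and its timing, and r may be low. This stands: at r = 0.2 or below the formula gain is at most 1.6 points, and the larger figures need r of 0.5 or more, which nothing in the documents supports.

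Third, the choice of model matters. With skewed or floored data, linear ANCOVA on the raw distance can do worse than the planned test. In simulation at r = 0.5 its power was 72% against 82% (lognormal) and 58% against 73% (skewed, about 40% at zero). This rules out linear ANCOVA on raw distance as the default, but not an ordinal model.

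Fourth, the half-widths above are on the SD scale and do not describe the interval for an odds ratio. An odds ratio is also not on the distance scale that readers would use. Both points are right, and they are the reason to report the Hodges-Lehmann shift as well.

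Fifth, the 15.1% applies only to unbalanced trials at r = 0.6; overall the planned test holds its level. That is also correct. The figure describes the result in an unlucky trial, not a fault of the test on average.

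Finally, the confounder line sits under the exclusion criteria. If such patients are excluded, there is nothing to adjust for. The main point does not depend on that line.

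**Conclusion.** The concern holds as an efficiency and reporting weakness; there is no error in the test or in the sample size. On near-normal data, adjustment for the outcome's own enrollment value is worth about 2 points of power at r = 0.2, 3 to 4 at r = 0.3 and 10 at r = 0.5. It is worth less if the distance is skewed with many zeros. At r = 0 it cost essentially no power in any simulated case of the ordinal model. It also largely removes the effect of a chance baseline difference on the type I error.

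These sizes rest on 1:1 allocation, 67 analysed per arm, an effect of 0.50 SD, the simulated distributions and an assumed r. The missing effect estimate and CI need attention whatever r turns out to be.

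**What to change.** 1. **Primary analysis.** Fit a proportional-odds regression of 6-week finger-to-crease distance on arm and enrollment distance. Use one prespecified score per patient, stating how fingers II–V are combined. Report the treatment odds ratio with a 95% CI.
2. **Other outcomes.** Use the same form of model for PROMIS upper extremity function, pain interference and pain, each with its own enrollment value.
3. **Sensitivity analysis.** Keep the Wilcoxon-Mann-Whitney test, with a Hodges-Lehmann shift and 95% CI.
4. **Operative versus nonoperative treatment.** Add it as a covariate only if it is recorded and settled before randomisation.
5. **Missing enrollment values.** State a rule that does not drop randomised patients and is the same in both arms.
6. **Separately**, list the factors and the model for the associated-factors hypothesis, and say whether the two characteristics labelled confounders are among them.

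The cost is analysis wording only. The enrollment values are already scheduled, and no extra patients or visits are needed. Operative status is not on the Measured variables list, so item 4 applies only if it is captured.

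### Does the primary test need a stated rule for turning four finger distances into one value per patient?

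*Combined protocol and SAP*

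**What the plan says.** The primary null hypothesis, under Specific Aims, concerns one quantity at one time: "There is no difference in finger stiffness (distance to palmar crease) between patients taking vitamin C or placebo after six weeks". Study Procedures gives the measurements at enrollment and at six weeks as "we will measure: DPC (dig II-V), PROMIS UE CAT, PROMIS pain interference and VAS score". The list of measured variables has a single entry for this outcome, beginning "Finger tip distance to palmar crease of fingers II-V (DPC".

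Under Biostatistical Analyses, the whole comparison is one sentence: "Difference in DPC, function, pain interference and pain will be assessed by Wilcoxon-Mann-Whitney test". The sample size follows: "power analysis suggests 134 patients provide 80% power to detect a difference with an alpha of 0.05", with the bracketed inputs "effect size 0.50, two tailed Wilcoxon-Mann-Whitney test". The 0.50 is attributed to previous studies. It carries no unit, standard deviation or named variable.

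On blinding, Subject Enrollment says that the "pharmacist will be the only person with access to the code until conclusion of the trial".

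**The concern.** The Wilcoxon-Mann-Whitney test compares independent observations, so it needs one value from each patient. The plan collects four and gives no rule for combining them. A mean, a sum, the worst finger, one chosen finger and four separate tests would all fit the words about measurement. Two analysts could therefore run different primary tests on the same data.

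Two things would be at stake. The first is the type I error: if four fingers were each tested at 0.05 and any significant one were counted, or if fingers were treated as independent units, the stated 0.05 would not hold. The second is power: 80% applies to whichever variable has the 0.50 effect, and that variable is not named.

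**Working it through.** **1. The plan's own figure.** Inputs from Biostatistical Analyses: effect size d = 0.50, two-sided alpha 0.05, power 80%, total 134. Equal allocation (67 per arm) is assumed, because no ratio is stated.

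- Effective size per arm, using the Wilcoxon efficiency for normal data: 67 × 3/π = 63.98.
- Noncentrality: 0.50 × √(63.98/2) = 2.828.
- Degrees of freedom: 2 × 63.98 − 2 = 125.96, critical value 1.979.
- Power from the noncentral t: 80.1%. A direct simulation of the rank test gave 80.2%.

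So 134 is right for one value per patient, tested once at 0.05.

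**2. Type I error by reading.** Simulation with 67 per arm, no true effect, between-finger correlation ρ of 0.5 to 0.9, and 0% to 60% of values at zero. Both ranges are assumptions; the documents give neither.

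| Analysis | False-positive rate |
|---|---|
| One value named in advance (one finger, mean or worst finger) | 4.6% to 5.4% |
| Smaller p-value of mean and worst finger, chosen afterwards | 5.3% to 6.8% |
| Any of four fingers at 0.05, uncorrected | 9% to 17% |
| Fingers counted as independent (268 vs 268) | 18% to 31% |

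For scale, four independent tests would give 1 − 0.95⁴ = 18.5%.

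**3. Which readings the text supports.** The hypothesis is a single comparison between patients. The variable list treats the four fingers as one entry with one label. The sample size counts patients and reproduces only for one test at 0.05. Four tests with a Bonferroni correction (0.05/4 = 0.0125, d = 0.50 per finger) would have 62% power at 134 and need about 190 patients. The last row of the table contradicts the plan's unit of analysis. The row above it is not excluded by the text, but nothing announces it.

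**4. Power by reading.** Assume equally correlated normal finger values, the same shift on each finger and no floor at zero. The standard deviation of the four-finger mean is then √((1 + 3ρ)/4) times that of one finger: 0.791, 0.880 and 0.962 at ρ = 0.5, 0.7 and 0.9.

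- If 0.50 describes the mean, one finger has d = 0.50 × that factor = 0.395, 0.440, 0.481.
- If 0.50 describes each finger, the mean has d = 0.50 ÷ that factor = 0.632, 0.568, 0.520.

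Power at 134 for ρ = 0.5 / 0.7 / 0.9:

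| Value tested | 0.50 describes the mean | 0.50 describes each finger |
|---|---|---|
| Mean of four | about 80% throughout | 94 / 89 / 83% |
| Worst finger | 74 / 76 / 78% | 91 / 86 / 82% |
| One finger | 60 / 70 / 77% | about 80% throughout |

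The open definition can move power either way. Across both columns the mean is never materially below the stated 80%, and the worst finger falls at most about 6 points short (80 − 74).

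**5. How often two readings disagree.** With a true effect of 0.50 in the mean, mean and worst finger differ on significance in 5% to 11% of trials, and mean and one finger in 7% to 25%. With no true effect the corresponding figures are about 1% to 3% and 3% to 6%.

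**The case for a change.** The strongest case for a change is that this is the only primary outcome. The trial was also set up to replace a subjective diagnosis with an objective measurement, so its one confirmatory variable should be defined beyond dispute. A sentence would cost no patients, visits or measurements. Nothing in the document says that the investigators will average, and the effect size cannot be used to work back to the intended variable: it is credited to a trial whose listed title concerns the frequency of reflex sympathetic dystrophy.

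Much of this stands as fact. The definition is absent, and neither redaction nor text extraction explains it. Picking one favourable finger after seeing the results would be a genuine abuse that the text does not expressly forbid. The disagreement between the mean and a single finger is also not trivial when there is a true effect.

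It does not amount to a fault in the design. The remedy would only write down a choice that any analyst must make before running the test, and either of the natural summaries is acceptable. Adding that 0.50 refers to that summary would supply neither a DPC difference nor a standard deviation, so the effect size would be no better justified than before. Because the pharmacist alone holds the code until the trial concludes, the summary can be settled blind up to that point; the documents do not say whether the code has been released. The absence of a planned estimate or interval beside the p-value is a separate reporting matter.

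**Conclusion.** This is a missing detail that analysts fill sensibly, and no change follows. The plan fixes the outcome, the six-week time point, the two-tailed rank test and alpha 0.05. Its hypothesis and its sample size both point to one value per patient tested once. On that reading 134 patients give 80.1% power, and the false-positive rate stays near 5% whichever sensible summary is used; a later choice between mean and worst finger raises it only to about 5% to 7%.

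What remains uncertain is power: about 60% to 80% at 134 if 0.50 describes the four-finger mean, and about 80% to 94% if it describes each finger, depending on the value tested. These ranges rest on assumed correlations of 0.5 to 0.9, normal values and an equal effect on all four fingers. Skewed distances with many zeros would shift them. The conclusion would differ if four uncorrected finger tests, or fingers pooled as independent units, were actually planned, and the documents announce neither.

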Adverse effects of vitamin C are dose-dependent and occur at doses well above the recommended daily dose of 60 mg. Generally, adverse side effects can be avoided with doses below 1000 mg daily in healthy people.¹⁴ In this study, patients who receive the vitamin C treatment will only take 500 mg daily. When several grams of vitamin C are taken at once, diarrhea and abdominal bloating are the most frequent side effects. In addition, renal calculi can precipitate as a result of the ingestion of excess vitamin C. Oxalic acid is produced and renally excreted during vitamin C metabolism. In patients with underlying hyperoxaluria, oxalate excretion is accelerated with vitamin C doses above 1000 mg daily and can contribute to formation of renal calculi. Similarly, hyperuricosuria can occur with large doses of vitamin C, also leading to formation of renal calculi. In patients requiring dialysis, hyperoxalemia can occur with doses as low as 500 mg daily. Therefore, these patients are excluded from our study.

The subject will be inconvenienced by having to complete study related questionnaires and physical examination (about 20 minutes).

POTENTIAL BENEFIT

There may or may not be any direct benefits to the individual subjects. Subjects may benefit from the Vitamin C treatment by experiencing reduced pain and reduced finger stiffness. It is also possible that the subjects will not directly benefit from the treatment, and will recover from their injury as they would under the standard of care treatment outside of this research. Either outcome will contribute to the understanding of the role of vitamin C in the healing of distal radius fractures.

MONITORING AND QUALITY ASSURANCE

Any adverse events will be recorded by a full time research coordinator involved in this project and discussed with the PI immediately. An overview of all adverse events will be discussed at the monthly research meeting at which the PI will decide whether to continue or alter/stop the trial.

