The PI will have overall responsibility for the conduct and monitoring of the study and safety of subjects. The research coordinator has an assistive role and will monitor outcomes on a daily basis. The research coordinator will have an assistive role and will be responsible for monitoring outcomes on a daily basis and the research coordinator will discuss all outcomes with the PI on a monthly basis at the research meeting. No independent monitoring will occur. All investigators and study staff will be responsible for reporting adverse effects to the research coordinator. Should any adverse events occur, the research coordinator will report such events to the PI immediately. The research coordinator will report adverse events to the IRB in accordance with the IRB adverse event reporting procedures.

There will be a full-time research coordinator responsible for adherence to all IRB rules and guidelines and for the accuracy and completeness of all forms, entries, and

informed consent. The research coordinator is responsible for monitoring all data and adherence to the IRB-approved protocol on a daily basis, and all data and study details will be reviewed with the PI at the monthly research meeting. The research coordinator will report any deviations from the protocol to the PI immediately.

All data from subjects will be filed in locked cabinets in the research office in individualized research folders, independent of clinical charts or any other medical record in electronic format. Any magnetic or electronic information will be saved in password-protected computers to which only research coordinator and persons involved with the research project will have access.

All participants are given a participation number/code at the time of enrollment matching with their received medication box. This code is kept on all data sheets instead of the patient name. Subject information is only accessible by Partners authorized investigators and will not be shared with outside entities. The final results after statistical analysis will not be shared with the any institution.

REFERENCES

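### The monthly continue/alter/stop decision uses adverse events, but no scheduled measurement or contact is stated to ask patients about them, so capture is largely unsolicited and probably incomplete

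*Combined protocol and SAP*

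**What the plan says.** The section Monitoring and Quality Assurance states that "Any adverse events will be recorded by a full time research coordinator involved in this project and discussed with the PI immediately". A summary of all events goes to a monthly research meeting, where the principal investigator decides whether the trial continues, is altered or stops. The same section adds that "All investigators and study staff will be responsible for reporting adverse effects to the research coordinator", that events are passed to the IRB under its procedures, and that there is no independent monitoring.

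Under Study Procedures, at enrollment and 6 weeks (5 to 8 weeks after fracture) "we will measure: DPC (dig II-V), PROMIS UE CAT, PROMIS pain interference and VAS score". The Measured variables list gives the same domains for those times, and PROMIS upper extremity function and the 0-10 pain rating at 6 months. Patients missed at 6 weeks are pursued by email and telephone to complete the questionnaires. The 6-month contact is by email, with telephone for those who do not respond.

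Risks and Discomforts says that "diarrhea and abdominal bloating are the most frequent side effects", but ties this to several grams taken at once. It links renal calculi to excess or large intake. It also says that side effects can generally be avoided below 1000 mg daily in healthy people, and that trial patients take 500 mg daily. Biostatistical Analyses covers the efficacy outcomes and plans no tabulation of adverse events by arm.

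**The concern.** The plan sets out what happens after staff know of an event: who writes it down, who is told, and who decides. It does not say how staff come to know. Neither account of the measurements contains an adverse-event question, symptom checklist or diary. No study contact is scheduled between enrollment and the 6-week assessment, and the stated purpose of the later email and telephone contacts is to complete outcome questionnaires.

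Diarrhea, bloating, or a renal stone treated elsewhere would not show themselves to staff measuring finger motion and arm function. Such events are likely to be under-counted in the record that feeds the monthly decision. A low or zero count would then be hard to interpret, since it could mean few events or few questions. Symptoms that were never asked about cannot be recovered at analysis.

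**Working it through.** **Plan's own figure.** The plan states that "134 patients provide 80% power to detect a difference with an alpha of 0.05" ("effect size 0.50, two tailed Wilcoxon-Mann-Whitney test"). The normal approximation gives 2 × ((1.960 + 0.842)/0.50)² = 62.8 per arm. Dividing by the Wilcoxon efficiency 3/π = 0.955 gives 65.8, so 66 per arm. Noncentral t power with n scaled by 0.955 first reaches 80% at 67 per arm (80.1%), a total of 134. The stated size reproduces and is not in dispute; it only supplies the arm size below. The 1:1 ratio is an assumption, because the text says only that the pharmacist will "randomize the boxes of medication according to a list of generated random numbers". The figure of 67 also allows for no dropout.

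**Chance of recording no event.** Let p be the true event rate in the vitamin C arm and c the share of events that reach the record. With 67 patients, P(none recorded) = (1 − p·c)^67. The documents give neither p nor c; all values here are assumptions.

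| True rate p | Expected affected (67 × p) | c = 100% | c = 50% | c = 25% |
|---|---|---|---|---|
| 10% | 6.7 | 0.90^67 = 0.1% | 0.95^67 = 3% | 0.975^67 = 18% |
| 5% | 3.4 | 0.95^67 = 3% | 0.975^67 = 18% | 0.9875^67 = 43% |
| 2% | 1.3 | 0.98^67 = 26% | 0.99^67 = 51% | 0.995^67 = 72% |

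**What zero recorded events would show.** With everyone asked and full capture, 0 of 67 gives a one-sided 95% upper bound of 1 − 0.05^(1/67) = 4.4%. With known capture c, the bound on the true rate is 4.37%/c: 8.7% at 50% and 17.5% at 25%. With unknown capture there is no usable bound.

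**Comparison between arms.** For assumed true rates of 15% against 5%, power with 67 per arm is about 49%, 26% and 15% at capture of 100%, 50% and 25%. A tabulation by arm would be descriptive even with full capture.

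**Timing of the 6-week question.** Enrollment is allowed up to two weeks after fracture and treatment lasts six weeks, so treatment can run to week 2 + 6 = 8 after fracture (if it starts at enrollment). The assessment is timed from fracture and may fall at week 5. A patient enrolled at week 2 and seen at week 5 has 8 − 5 = 3 weeks of treatment left, and the only later scheduled contact is the 6-month questionnaire.

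**The case against.** The strongest reply is that the protocol expects little to find. It attaches the gastrointestinal effects to several grams at once, regards side effects as generally avoidable below 1000 mg daily in healthy people, and excludes patients with kidney stones or severe kidney failure. This stands and limits the weight of the point. It does not remove it, because an expectation of few events is not a means of detecting them.

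Several stronger readings go beyond the text:

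- A reader might infer that the protocol predicts diarrhea, bloating and stones at the trial dose. It says roughly the opposite.
- A reader might infer that tolerability is known only from what patients volunteer. Staff must also report effects that they notice, and missed visits are followed up by telephone. Both routes still lack a stated question.
- A reader might infer that the forms have no place for an event. The measurement list is not shown to be exhaustive: dominant-side fracture and current vitamin C supplements are named under Subject Selection as baseline characteristics but do not appear in it. The REDCap forms are not in the supplied text, and consent pages were removed. The documents support only that no scheduled question is stated.
- A reader might infer that the trial fails to test its own remark about limited downside. That remark is background on risk; no aim or hypothesis concerns tolerability.
- A reader might infer that zero recorded events would carry no information. That holds only if capture is wholly unknown; otherwise the bound is looser, as shown.

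Blinding makes unequal under-reporting between arms unlikely. The cost is therefore mainly a low count and less ability to see a difference, rather than a biased comparison.

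**Conclusion.** The point holds in a limited form. Adverse events feed the continue/alter/stop decision, yet no scheduled measurement or contact is stated to ask about them. Capture is therefore largely unsolicited, and under-counting is probable but not demonstrated. Moving from full to quarter capture raises the chance of an empty vitamin C record from 0.1% to 18%, from 3% to 43%, or from 26% to 72%, at assumed true rates of 10%, 5% and 2%. These figures rest on assumed rates and capture, 1:1 allocation and no dropout; the gap itself rests only on the text. Given the protocol's low expectation at 500 mg daily, this is a modest improvement, worth making because it is cheap and cannot be made after the data are collected. Nothing here bears on the dose or on what the stopping rule should be.

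**What to change.** Add to the existing 6-week REDCap form, in the same words for both arms and for in-person, email and telephone completion:

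- one open question on any new health problem since enrollment;
- yes/no items for diarrhea, abdominal bloating, renal stone, and stopping study medication because of a problem.

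Repeat all items at 6 months, not just the renal-stone item, because some patients may still be on treatment at the 6-week visit. State in the protocol that these answers feed the adverse-event record reviewed monthly, and add to Biostatistical Analyses a descriptive tabulation by arm at trial end, with the number of patients asked as denominator.

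The cost is one open question and four yes/no items on each of two questionnaires already sent, with no extra visit. Prompting will raise reports of minor symptoms, but equally in both blinded arms. One limit remains: a question asked once at 6 weeks gives no early warning for an individual patient, so the existing staff reporting route is still needed.
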